### **Timing of the analyses:**

For each analysis, actual COD will be based on the actual date at which the minimum requirements in terms of number of events and follow-up are both met as described in the [Table 7](#) below. Per FDA request, the second interim analysis and the final analysis should be performed when at least 2 years and at least 3 years of follow-up have been observed for all patients, respectively.

**Table 7 - Timing of analyses**

Analysis	Number of events required	Minimum follow-up required	Expected COD
Interim analysis 1 IBCFS	Approximately 189	-	28 months after first patient is randomized
Interim analysis 2 IBCFS	Approximately 426	2 years	48 months after first patient is randomized
Final analysis IBCFS	Approximately 568	3 years	60 months after first patient is randomized
Long-term follow-up analysis 1	-	5 years	5 years after last patient is randomized
Long-term follow-up analysis 2	-	10 years	10 years after last patient is randomized

IBCFS = Invasive breast cancer-free survival; COD = Cut-off date

### **9.2.2 Primary endpoint**

Invasive breast cancer-free survival (IBCFS) is defined as the time from the date of randomization to the date of the first occurrence of one of the following events:

- Ipsilateral invasive breast tumor recurrence (IIBTR): invasive breast cancer involving the same breast parenchyma as the original primary.
- Local-regional invasive breast cancer recurrence: Invasive breast cancer in the axilla, regional lymph nodes, chest wall, and skin of the ipsilateral breast.
- Distant recurrence: Metastatic disease-breast cancer that has either been biopsy confirmed or clinically diagnosed as recurrent invasive breast cancer.
- Death attributable to any cause, including breast cancer, non-breast cancer, or unknown cause.
- Invasive contralateral breast cancer.

A summary of the primary estimand associated with the primary endpoint is provided in [Table 8](#).

**Table 8 - Summary of primary estimand of the primary endpoint**

Endpoint Category (estimand)	Estimands			
	Endpoint	Population	Intercurrent event(s) handling strategy	Population-level summary (Analysis and missing data handling)
Primary objective: to determine whether amcnestrant once a day (QD) improves the IDFS excluding second primary invasive cancers of non-breast origin (IBCFS) when compared to tamoxifen QD in patients with early breast cancer as adjuvant treatment				
Primary endpoint (Estimand 1)	IBCFS	ITT	
Interruption/discontinuation of study intervention: IBCFS will be analyzed based on disease assessments irrespective of study intervention interruption/discontinuation (treatment policy strategy).
 
Start of new therapy prior to IBCFS event: IBCFS will be analyzed based on disease assessments regardless of whether new therapy is initiated prior to event of interest (treatment policy strategy).
 
IBCFS event documented more than 12m+90days after previous disease assessment: IBCFS will be censored at the last disease assessment prior to the event (hypothetical strategy).
	
One-sided log-rank test stratified by randomization stratification factors (except geographical regions), as entered in the IRT system.
 
Hazard ratio (HR) and corresponding CI estimated using stratified Cox proportional hazard model
 
The Kaplan Meier estimate of event free probabilities at specified time points, quartiles and corresponding 95% CI from Kaplan Meier method

Primary efficacy analysis will consist of IBCFS comparison between the amcnestrant arm and the tamoxifen arm through a logrank test procedure stratified by the stratification factors (except geographic region to minimize the risk of power loss due to large number of strata and potentially low number of events in some strata) as entered in the IRT. A one-sided Type I error rate of 2.5% will be used for statistical testing.

The primary analysis of IBCFS will be based on the following censoring rules:

- If none of the IBCFS event is observed before the IBCFS analysis COD, participants will be censored at the date of the last disease assessment documenting no IBCFS event before the COD.
- A participant without an IBCFS event and without any valid postbaseline disease assessments will be censored at the day of randomization (Day 1).
- An IBCFS event documented after more than 12 months + 90 days following randomization or the previous disease assessment, whichever is later, will be censored at the date of the last disease assessment documenting no IBCFS event prior to the documented IBCFS event or the date of randomization, whichever is later. Twelve months + 90 days is the longest allowed interval between visits in this trial as defined in the schedule of activities.

The HR estimates and corresponding confidence intervals will be provided using the Cox proportional hazard model stratified by the same stratification factors as those used for the logrank test described above. The IBCFS quantiles and IBCFS rates at different time points (calculated using the Kaplan-Meier methods) as well as corresponding 95% CIs will be presented by treatment arm. The Kaplan-Meier IBCFS curves will also be provided.

Sensitivity, supportive and subgroup analyses of IBCFS will be performed as specified in the SAP.

Two interim analyses at 1/3 (approximately 189 IBCFS events, non-binding futility only) and 3/4 (approximately 426 IBCFS events, efficacy and non-binding futility) of the target number of events (approximately 568 IBCFS events) are planned. The primary IBCFS analysis corresponds either to a positive interim IBCFS analysis or the final IBCFS analysis. Detail of the interim analyses are provided in [Section 9.3](#).

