### **2.2.8 Rationale for the assumption in the tamoxifen arm**

The intention of AMEERA-6 trial is to determine whether amcnestrant compared with tamoxifen improves IBCFS in patients who discontinued prior AI due to treatment-related toxicities. For the purpose of this study, patients diagnosed with early-stage breast cancer who are at high risk of disease recurrence will be selected.

Regarding justification and rationale for the statistical assumption of the performance of participants treated on the tamoxifen arm in AMEERA-6, namely 4-year IBCFS of 82%, data from historical as well as more contemporaneous studies is informative.

In the BIG 1-98 study (46), wherein the high-risk population represented 41% of the global trial population, the 5-year DFS among patients with node positive cancer was 77.9% in the letrozole-only group in comparison with 71.4% in the tamoxifen-only group.

Meanwhile, more recent adjuvant trials in patients with ER+/HER2- early breast cancer evaluated the combination of CDK4/6-inhibitors with endocrine therapy as compared to standard endocrine therapies.

In the PALLAS study, eligible patients were randomly assigned to receive palbociclib for 2 years plus endocrine therapy or standard endocrine therapy with or without an LHRH agonist. Primary endpoint was IDFS using STEEP definition and IBCFS was defined as a correlative and exploratory endpoint. Adjuvant endocrine therapy selection included 3872 (67.2%) of 5760 patients initiating an AI, 1872 (32.5%) patients initiating tamoxifen, and 1136 (19.7%) patients receiving a concurrent LHRH agonist, similarly in both treatment arms. Among the 5760 randomized patients, 3382 (58.7%) had high clinical risk, defined as more than 4 positive nodes, or one to three positive nodes either T3 or T4, or Grade 3 disease, or both. Results of the second interim analyses were reported recently. Invasive DFS did not statistically differ between the two groups, with a 3-year IDFS of 88.2% (95% CI 85.2-90.6) in the palbociclib plus endocrine therapy group, and 88.5% (85.8-90.7) in the endocrine therapy alone group (HR 0.93 [95% CI 0.76-1.15]; logrank  $p = 0.51$ ). When considering the exploratory endpoint of IBCFS, the 3-year IBCFS rate was 89.5% (95% CI 86.9-91.7) in the endocrine therapy alone group. In the high-risk clinical group, the 3-year IDFS rate was 83.6% (95% CI 78.7-87.7) in the endocrine therapy alone group (51).

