#### Type of participant and disease characteristics

- I 02. Participants with histologically confirmed diagnosis of adenocarcinoma of the breast with documentation of ER+ ( $\geq 10\%$  positive stained cells) and/or PgR+ ( $\geq 10\%$  positive stained cells) based on invasive breast tumor cell staining by immunohistochemistry (IHC) assay consistent with central assessment. If axillary lymph nodes are tested, ER and/or PgR must also be positive.
- Participants with bilateral invasive disease are allowed only if the contralateral breast tumor meet the criteria regarding ER and PgR-status described above.
  - In case of multicentric or multifocal or synchronous bilateral breast cancer, the lesion considered at highest risk for recurrence based on the investigators' discretion will be used for central pathology review and stratification.
- I 03. Participants irrespective of HER-2 status (HER2-positive, HER2-negative, unknown) as assessed per ASCO/College of American Pathologist guidelines (59), are eligible provided in each case they meet the ER and PgR criteria in I 02.
- HER2-negative is defined as a score of 0, 1+ by IHC or a negative in situ hybridization (ISH) based on single-probe average HER2 copy number
  - HER2-positive is defined as a score of 3+ by IHC or a positive ISH based on single-probe average HER2 copy number. All adjuvant anti-HER2 treatment and chemotherapy must be completed prior to randomization.
- I 04. Participants with Stage IIB or Stage III invasive breast cancer per the AJCC Cancer Anatomic Staging 8th edition who have undergone adequate (definitive) breast surgery and adjuvant radiation (if indicated) for the current malignancy. Participants with inflammatory breast cancer are not eligible.
- In participants having received upfront surgery with or without adjuvant systemic therapy, eligibility is based on pathological staging (pTNM) rather than clinical staging (cTNM), in case there is a discordancy between these.

- If neoadjuvant systemic therapy was administered, participants must have Stage IIB or Stage III invasive breast cancer based on clinical staging (cTNM) and have residual nodal disease after definitive breast surgery (ypN1-3).
- Participants with only residual micrometastatic disease (N1mic) or isolated tumor cells (ITCs) in the axillary lymph nodes are not eligible.

NOTE: the One-Step Nucleic Acid Amplification (OSNA) method is acceptable for sentinel lymph-node assessment.

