#### 9.4 SAMPLE SIZE DETERMINATION

For IBCFS, a total of 568 IBCFS events will be needed to reject the null hypothesis using a log-rank test at the one-sided level of 2.5% and 90% power under the assumption of an HR of 0.76. Assuming proportional hazards under an exponential model and based on an anticipated 4-year IBCFS rate of 82% in the tamoxifen arm, this is expected to correspond to a 4-year IBCFS rate of 86% in the amcenestrant arm.

Based on a piecewise enrollment assumption over 24 months as described in [Table 12](#), an IBCFS cut-off date (COD) 60 months after the first participant randomized and an annual dropout rate of 1%, a total of 3738 participants are expected to be randomized in a 1:1 ratio into the amcenestrant and tamoxifen arms.

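### The primary IBCFS test and hazard ratio leave out stage; prespecifying it as a covariate could add roughly 0 to 1.5 points of power (a low-severity refinement, not an error)

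*Combined protocol and SAP*

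**What the plan says.** - **Randomization (Section 4.1).** There are five factors: duration of prior AI exposure (2 levels), prior chemotherapy combined with HER2 status (3), prior CDK4/6 inhibitor (2), region, and sex/menopausal group (2). None is stage, tumor size or nodal status.
- **Primary analysis (Section 9.2.2 and Table 8).** The log-rank test is "stratified by the stratification factors (except geographic region to minimize the risk of power loss due to large number of strata" and sparse events in some of them). The Cox hazard ratio uses the same factors. That leaves 2 × 3 × 2 × 2 = 24 strata, and no covariate is named.
- **Design target (Section 9.4).** "a total of 568 IBCFS events will be needed to reject the null hypothesis using a log-rank test at the one-sided level of 2.5" per cent, with "90% power under the assumption of an HR of 0.76".
- **Stage (Section 5.1, I 04).** Eligible are "Participants with Stage IIB or Stage III invasive breast cancer per the AJCC Cancer Anatomic Staging 8th edition". Pathological staging governs after upfront surgery. After neoadjuvant therapy, the criterion is clinical stage plus residual nodal disease.
- **Stage as a risk marker (Section 8.1.1).** Patients at stage IIIA or above who have not yet been staged are among those counted at highest clinical risk. The protocol therefore draws a risk line inside its own eligible range.
- **What is left open (Sections 9.2 and 9.2.2).** Sensitivity, supportive and subgroup analyses are deferred to an SAP to be finalized before the first database lock. The document supplied contains no separate SAP text.

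**The concern.** Stage is needed to enroll anyone, and the protocol treats it as a marker of recurrence risk, yet the primary analysis does not use it. Omitting a prognostic covariate from a time-to-event comparison has two effects. The hazard ratio moves slightly toward 1, with some loss of power. Any chance difference in stage mix between the arms also stays in the test statistic. The reason given for dropping region, too many strata, does not apply to a covariate, because a covariate adds no strata. If an imbalance is noticed only after unblinding, adjusting for it is post hoc.

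**Working it through.** **1. Reproduce the plan.** Inputs from Sections 9.3 and 9.4: HR 0.76, one-sided 2.5%, 90% power, "an anticipated 4-year IBCFS rate of 82% in the tamoxifen arm", Table 12 accrual, and "an annual dropout rate of 1%, a total of 3738 participants are expected to be randomized in a 1:1 ratio".

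- Fixed design: events = 4(1.960 + 1.282)² / (ln 0.76)² = 4 × 10.507 / 0.0753 ≈ 558, taken as 559.
- With one O'Brien-Fleming-type efficacy look at 426 of 568 events and non-binding futility ignored: 567.5, i.e. 568 events, and 90.0% power.
- Power at the second interim analysis is 68.9% (Table 11: 69%). Boundaries are p = 0.0096 and 0.0221, at HR 0.797 and 0.845 (Table 11: 0.7971 and 0.8447).
- Expected events are 189, 427 and 568 at months 28, 47.5 and 60. The amcenestrant 4-year rate is 0.82^0.76 = 86.0%.

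The design is internally sound.

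**2. What the protocol's figures say about prognosis.** Section 2.2.8 has two contrasts, both from other trials.

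- Adjuvant palbociclib trial (PALLAS), endocrine-only arm: "In the high-risk clinical group, the 3-year IDFS rate was 83.6" per cent, against 88.5% overall, with 58.7% of patients at high risk. Implied rate in the rest: (88.5 − 0.587 × 83.6) / 0.413 = 95.5%. Implied HR: ln 0.836 / ln 0.955 ≈ 3.9.
- Letrozole-versus-tamoxifen trial (BIG 1-98): 71.4% in node-positive tamoxifen patients and 81.4% overall (Section 2.2.3), assuming that the stated 41% high-risk share is the node-positive share. Rest: (81.4 − 0.41 × 71.4) / 0.59 = 88.3%. HR: ln 0.714 / ln 0.883 ≈ 2.7.

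Neither is a within-IIB-III contrast, so the range examined below is 1.5 to 3.9.

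**3. Power with and without stage.** 8,000 simulated trials per row, with the plan's accrual and dropout, 24 strata, looks at 426 and 568 events, and HR 0.76 conditional on stage. Stage is two-level here. Correlated means that prior chemotherapy and CDK4/6 use were made to depend on stage.

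| Assumed stage HR (share in higher group) | Existing strata vs stage | Power, plan | Power, plan + covariate | Gain, points (SE) | Gain as extra strata (SE) |
|---|---|---|---|---|---|
| 1.0 (50%) | independent | 90.09% | 90.04% | −0.05 (0.04) | −0.07 (0.12) |
| 1.5 (50%) | correlated | 89.54% | 89.58% | +0.04 (0.12) | −0.26 (0.14) |
| 2.0 (50%) | independent | 89.40% | 89.92% | +0.53 (0.17) | +0.35 (0.18) |
| 2.0 (50%) | correlated | 89.25% | 89.61% | +0.36 (0.16) | +0.25 (0.17) |
| 2.7 (41%) | correlated | 89.11% | 89.84% | +0.73 (0.18) | +0.66 (0.19) |
| 3.9 (59%) | independent | 88.25% | 89.56% | +1.31 (0.21) | +1.24 (0.22) |
| 3.9 (59%) | correlated | 88.00% | 89.12% | +1.12 (0.21) | +0.76 (0.22) |

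Gains are from paired trials before rounding. An analytic calculation gives +0.2, +0.55 and +1.1 points at HR 1.5, 2.0 and 2.7 (50/50), and +1.5 at HR 3.9 in 59%. One skewed case, HR 3.9 in only 30%, gives +2.6. The unadjusted HR is about 0.762 to 0.765 instead of 0.76 for stage HRs of 2 to 3.9.

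**4. Three levels.** With an assumed mix of IIB 40%, IIIA 38% and IIIB-C 22%, 400 paired trials per scenario show the mean z rising by 0.026 (SE 0.007) at hazards 1:1.5:2.25 and by 0.073 (SE 0.012) at 1:2:4. Near 90% power these are worth about 0.5 and 1.3 points.

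**5. Chance imbalance.** With 1,869 per arm, the between-arm difference in a 40% stage category has SD √(0.4 × 0.6 × 2 / 1869) = 1.6 percentage points. In the step 4 trials, adjusting for stage changes z by an SD of 0.13 to 0.24. The final boundary of 0.0221 is z ≈ 2.01.

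**The case against.** The strongest reply is that nothing is broken. A log-rank test stratified by randomization factors is valid, and the power claim reproduces. The 0.76 follows from overall 4-year rates of 82% and 86%, so it is already averaged over stage and no power is lost against the plan's own target. Chance imbalance is symmetric and already covered by the Type I error. That two valid tests differ by 0.13 to 0.24 in z does not make the planned one defective. All of this stands.

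A reader might infer that stage is the strongest prognostic factor in the protocol's figures. The documents do not support that: they give no comparable contrast for any stratification factor, so nothing can be ranked. The 3.9 and 2.7 compare high-risk patients with lower-risk or node-negative ones, most of whom I 04 excludes, and the PALLAS group also mixes in grade. The 3.9 is imprecise as well. Holding 88.5% fixed, the printed confidence limits for 83.6% (78.7 and 87.7) move the rate in the rest from an impossible 102% to 89.6%, where the HR is 1.2. This is crude, since the two rates are correlated.

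A reader might also infer that adjustment is entirely free. It needs no extra patients or events. As extra strata, however, it would double 24 cells to 48 even for a two-level variable, and at a stage HR of 1.5 the point estimate is a small loss. As a covariate it makes the HR conditional on stage and needs one definition across two staging bases.

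Finally, the SAP may already plan a stage-adjusted supportive analysis. That cannot be ruled out, but the primary test as specified in Section 9.2.2 has none.

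**Conclusion.** The point holds as a low-severity efficiency improvement. The primary test and HR carry no stage or nodal term, although stage must be known for all participants. Prespecifying stage as a covariate could add roughly 0 to 1.5 points of power and would remove chance stage imbalance from the primary result. The range rests on an assumed stage HR of about 1.5 to 3.9 and assumed stage shares. The skewed case at +2.6 lies outside it and takes its HR from a broader-risk population. Overlap between stage and the existing strata trims the gain. A firm minimum gain cannot be claimed: at a stage HR of 1.5 it is 0 to 0.2 points. The attenuation of the HR is slight. That Type I error is preserved rests on the covariate being a prespecified baseline variable; no simulation under equal arms was run.

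**What to change.** Before the first database lock:

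1. Define one baseline stage variable (IIB, IIIA, IIIB-C). State which staging basis applies after upfront surgery (pTNM) and after neoadjuvant therapy (cTNM, and how ypN enters). Confirm that the eCRF captures the components.
2. Add it as a covariate to the Cox model stratified by the four IRT factors, use that model for the HR, and base the primary p-value on the matching stratified score test.
3. Keep the four-factor log-rank test as a sensitivity analysis.
4. Carry the change through Section 9.2.2, Table 8, the synopsis, and the IDFS analysis (Tables 9 and 10), which follows the same methods.
5. In Section 9.3, state which HR is compared with the futility limits of 1.2 and 1.1, since those use the stratified Cox estimate.

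The cost is protocol and SAP wording plus the stage definition, with no added patients, events or strata. The reported HR becomes stage-conditional and should be labeled so. If the sponsor prefers to keep the primary test as it is, a named, prespecified stage-adjusted analysis would be the minimum.

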NIMP: GnRH analog		↔							- Goserelin or other GnRH analog approved for use in early breast cancer as per site/ country availability - In men and pre/perimenopausal women

Procedure	Screening Period	Treatment Period [5 years – C1-C65]					EOT	Follow-up Period	Notes
		0	1	2	3	4-10 Q12 weeks			
Patient Visit #	Baseline	C1 D1	C2 D1	C4 D1	C7, C10, C13, C16, C19, C22, C25 D1	C28, C34, C40, C46, C52, C58 D1	D30 after last IMP dose	Q12 months after last IMP dose	
Patient Cycle Visit #	Up to 28 days before randomization	±3	±3	±7	±7	±7	±7	±45	
AE/SAE review	←=====→							X (ongoing related AEs, AESI, ongoing SAEs at EOT and new related AE/SAEs)	
Concomitant medication review	←=====→							X (related to AE/SAEs listed above)	From the date of informed consent form up to 30 days after the last dose of study treatment
Disease assessments:									
Disease recurrence assessment	X								At every visit and as clinically indicated until the detection of locoregional recurrence and distant recurrences (whichever comes last) or end of follow-up period, whichever comes first.

Procedure	Screening Period	Treatment Period [5 years – C1-C65]					EOT	Follow-up Period	Notes
		0	1	2	3	4-10 Q12 weeks			
Patient Visit #	Baseline	C1 D1	C2 D1	C4 D1	C7, C10, C13, C16, C19, C22, C25 D1	C28, C34, C40, C46, C52, C58 D1	D30 after last IMP dose	Q12 months after last IMP dose	
Patient Cycle Visit #	Up to 28 days before randomization	±3	±3	±7	±7	±7	±7	±45	
Time Window (day)									
Mammogram	X a				X b				
a. Screening: to be done if not already done in the past 6 months prior to randomization.
 
If local investigator plans to use MRIs instead of mammograms during the study, MRI will have to be performed at baseline
 
b. Post baseline: yearly from randomization (±30 days), and as clinically indicated until the detection of locoregional recurrence and distant recurrences (whichever comes last) or end of follow-up period, whichever comes first.

Procedure	Screening Period	Treatment Period [5 years – C1-C65]					EOT	Follow-up Period	Notes
		0	1	2	3	4-10 Q12 weeks			
Patient Visit #	Baseline	C1 D1	C2 D1	C4 D1	C7, C10, C13, C16, C19, C22, C25 D1	C28, C34, C40, C46, C52, C58 D1	D30 after last IMP dose	Q12 months after last IMP dose	
Patient Cycle Visit #	Up to 28 days before randomization	±3	±3	±7	±7	±7	±7	±45	
Time Window (day)									

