Radionuclide Bone Scan Whole Body; CT Scan / MRI /PET-CT Ultrasound of Chest, Abdomen, Pelvis or any clinically indicated sites of disease; Clinical evaluation of superficial disease	(X a )				(X b )				
a. Screening: to be done for patients at highest clinical risk for disease recurrence as outlined in I 08 (Section 5.1), for patients with stage IIIA or higher as clinically indicated.
 
b. Post baseline: to be done as clinically indicated until the detection of locoregional recurrence and distant recurrences (whichever comes last) or end of follow-up period, whichever comes first.

Biopsy (disease recurrence proof)					(X)				Disease recurrence should be confirmed histologically whenever possible. For the locoregional recurrence including skin recurrence it is strongly recommended to perform a biopsy unless clinically contra-indicated.

Procedure	Screening Period	Treatment Period [5 years – C1-C65]					EOT	Follow-up Period	Notes
		0	1	2	3	4-10 Q12 weeks			
Patient Visit #	Baseline	C1 D1	C2 D1	C4 D1	C7, C10, C13, C16, C19, C22, C25 D1	C28, C34, C40, C46, C52, C58 D1	D30 after last IMP dose	Q12 months after last IMP dose	
Patient Cycle Visit #	Up to 28 days before randomization	±3	±3	±7	±7	±7	±7	±45	
Time Window (day)									
Overall Survival Follow-up								X	After discontinuation of study treatment, post-study survival status (including post-study anticancer therapies; disease recurrence for patients who complete or prematurely discontinue study treatment without disease recurrence) will be collected
Electronic PRO measures:									
EORTC QLQ-C30, EORTC QLQ-BR23, EORTC-QLQ-IL127, EQ-5D-5L, PGIS		X a					X b		a. Data collected prior to first IMP intake on device at site on D1 C1 or earlier if patient has no unrecovered acute toxic effects of prior AI therapy (see exclusion criteria 6). b. At each visit after the 1 st cycle (D1 C2-C58) during the treatment period, at EOT, and at the first two post-treatment follow up visits. Data collected on device at site.

Procedure	Screening Period	Treatment Period [5 years – C1-C65]					EOT	Follow-up Period	Notes
		0	1	2	3	4-10 Q12 weeks			
Patient Visit #	Baseline	C1 D1	C2 D1	C4 D1	C7, C10, C13, C16, C19, C22, C25 D1	C28, C34, C40, C46, C52, C58 D1	D30 after last IMP dose	Q12 months after last IMP dose	
Patient Cycle Visit #	Up to 28 days before randomization	±3	±3	±7	±7	±7	±7	±45	
Time Window (day)									

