### **8.1.2 Post baseline**

- **Mammogram/breast MRI**

Mammogram (or breast MRI) will be performed on yearly basis from randomization (± 30 days), and as clinically indicated until the detection of locoregional recurrence and distant recurrences (whichever comes last) or end of follow-up period, whichever comes first.

- **CT Scan/MRI/Other imaging**

The post baseline imaging work-up will be done as clinically indicated until the detection of locoregional recurrence and distant recurrences (whichever comes last) or end of follow-up period.

The imaging work-up can include: Radionuclide Bone Scan Whole Body, CT Scan, MRI, PET-CT, Ultrasound of Chest, Abdomen, Pelvis or any clinically indicated sites of disease and clinical evaluation of superficial disease.

- **Biopsy**

Disease recurrence should be confirmed histologically whenever possible.

Note: for the locoregional recurrence including skin recurrence it is recommended to perform a biopsy unless clinically contra-indicated.

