### **8.1.3 Overall survival follow-up**

After discontinuation of study treatment, follow-up visits will be performed every 12 months (±45 days) from the last dose of study treatment for survival status and collection of data on post-study anticancer therapies, and disease recurrence for patients who complete or prematurely discontinue study treatment without disease recurrence.

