**Table 9 - Summary of primary estimand of the key secondary endpoint**

Endpoint Category (estimand)	Estimands			
	Endpoint	Population	Intercurrent event(s) handling strategy	Population-level summary (Analysis and missing data handling)
Key secondary objective: to determine whether amcnestrant once a day (QD) improves the invasive disease-free survival (IDFS) when compared to tamoxifen QD in patients with early breast cancer as adjuvant treatment				
Key secondary endpoint (Estimand 2)	IDFS	ITT	
Interruption/discontinuation of study intervention: IDFS will be analyzed based on disease assessments irrespective of study intervention interruption/discontinuation (treatment policy strategy).
 
Start of new therapy prior to IDFS event: IDFS will be analyzed based on disease assessments regardless of whether new therapy is initiated prior to event of interest (treatment policy strategy).
 
IDFS event documented more than 12m+90days after previous disease assessment: IDFS will be censored at the last disease assessment prior to the event (hypothetical strategy).
	
One-sided log-rank test stratified by randomization stratification factors (except geographical regions), as entered in the IRT system.
 
Hazard ratio (HR) and corresponding 95% CI estimated using stratified Cox proportional hazard model
 
The Kaplan Meier estimate of event free probabilities at specified time points, quartiles and corresponding 95% CI from Kaplan Meier method

Analysis of the key secondary endpoint analysis will consist of IDFS comparison between the amcnestrant arm and the tamoxifen arm through a logrank test procedure stratified by the stratification factors (except geographic region to minimize the risk of power loss due to large number of strata and potentially low number of events in some strata) as entered in the IRT.

In order to ensure a strong control of the overall Type I error rate at a one-sided 2.5%, a hierarchical testing strategy will be used. In other words, comparison between arms on the IDFS will be performed only if the primary analysis of the IBCFS is statistically significant. Therefore, a maximum of one formal statistical comparison is planned for IDFS. Otherwise, IDFS will be analyzed descriptively as for other secondary efficacy endpoints.

Same statistical methods and censoring rules as defined for the IBCFS will be used. Sensitivity, supportive and subgroup analyses will be performed as specified in the SAP.

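### Event-free participants are censored at their last assessment while later events still count, so per-arm Kaplan-Meier IBCFS rates near the end of follow-up read low (about 0 to 1.8 points at 4 years); the test and HR are essentially unaffected

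*Combined protocol and SAP*

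**What the plan says.** All references are to the Combined protocol and SAP.

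- **Event-free participants (9.2.2, below Table 8):** "participants will be censored at the date of the last disease assessment documenting no IBCFS event before the COD".
- **Events after a long gap (9.2.2):** the only limit on a late event is the rule that begins "An IBCFS event documented after more than 12 months + 90 days following randomization or the previous disease assessment". An event inside that window counts. Death from any cause is itself an event.
- **When disease is assessed (Schedule of Activities, 1.3):** "At every visit and as clinically indicated until the detection of locoregional recurrence and distant recurrences". Section 8.1.2 adds: "The post baseline imaging work-up will be done as clinically indicated". Mammography is yearly.
- **Visit spacing:** every 24 weeks from C28 on treatment. After treatment, under 8.1.3, "follow-up visits will be performed every 12 months (±45 days) from the last dose of study treatment".
- **What is reported (9.2.2):** "The IBCFS quantiles and IBCFS rates at different time points (calculated using the Kaplan-Meier methods", with 95% confidence intervals, by arm. Table 8 lists these rates in the primary estimand's population-level summary.
- **Other endpoints:** for IDFS (9.2.3.1), "Same statistical methods and censoring rules as defined for the IBCFS will be used". DRFS and LRRFS take the same rules in 9.2.3.2.

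**The concern.** Take two participants randomized 46 months before the cut-off date (COD), both last seen at C46, about month 41.4. One dies or has a symptomatic recurrence at month 45 and is an event at month 45. The other is well and is censored at month 41.4. The stretch between last visit and COD thus supplies events but no event-free person-time.

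Kaplan-Meier needs a censoring time that does not depend on whether an event follows. Here the late risk sets are too small and the late hazard too high, even with perfect attendance. The 12 months + 90 days rule does not help, because ordinary gaps before the COD fall inside it.

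What is at stake is the absolute event-free rate in each arm. The trial is planned on 4-year rates of 82% and 86% (9.4). At the final COD, follow-up runs from 36 to 60 months, so 4 years lies in the affected stretch. A positive second interim analysis would be the primary analysis (9.2.2), and there the 3-year rate is exposed.

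**Working it through.** **1. Reproduce the design (9.4, Tables 11 and 12).** Tamoxifen hazard = -ln(0.82)/4 = 0.0496 per year. Times 0.76 = 0.0377, so the 4-year amcenestrant rate is exp(-4 × 0.0377) = 86.0%, as stated. Events needed: 559 (Schoenfeld) or 566 (Freedman), against 568. Expected events at months 28, 47.5 and 60 are 189, 427 and 568, against 189, 426 and 568 in Table 11. The inputs are therefore the plan's own.

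**2. Hand calculation: visits on nominal days, nobody stops treatment early, all events dated between visits, dropout ignored.** Day 1 of cycle c falls 28(c-1) days after the start, so C40, C46, C52 and C58 fall at months 35.9, 41.4, 46.9 and 52.4. With COD at month 60, a participant is followed to month t if randomized by month 60 - t. Let F be the cumulative share randomized, from Table 12 with straight lines between its points. Events at t come from the share F(60 - t). The event-free risk set holds only those followed to their next visit. The hazard is inflated by the ratio of the two.

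| Months | Mean share supplying events | Share in risk set | Ratio | Excess months of hazard |
|---|---|---|---|---|
| 35.88 to 41.40 | 86.8% | 73.0% | 1.19 | 1.04 |
| 41.40 to 46.92 | 59.2% | 45.4% | 1.30 | 1.68 |
| 46.92 to 48 | 42.7% | 21.5% | 1.98 | 1.06 |

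Total excess = 3.78 months.

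- Tamoxifen: 3.78 × 0.0496/12 = 0.0156; 82 × (1 - exp(-0.0156)) = 1.27 points.
- Amcenestrant: 3.78 × 0.0377/12 = 0.0119; 86 × (1 - exp(-0.0119)) = 1.02 points.

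Simulation of the same case (150,000 per arm, 1% annual dropout) gives 1.24 and 1.02 points against censoring at the COD. With half of the events between visits it gives 0.66 and 0.49.

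**3. Wider simulations of the 4-year rate at COD month 60 (true values 82.0% and 86.0%).** The share of events between visits and the discontinuation rate are assumptions. A rate of 8% per year is 1 - exp(-0.40) = 33% over 5 years. Monte Carlo error is roughly 0.15 points.

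| Scenario | Tamoxifen | Amcenestrant |
|---|---|---|
| 8%/year stop, all events between visits | 80.2-80.5% | 84.5-84.7% |
| 8%/year stop, half between visits | 81.2% | 85.1-85.3% |
| As above (half or all), yearly mammograms also count | 80.9-81.5% | 85.1-85.5% |
| 8%/year stop, none between visits, visits on nominal days | 81.8% | 86.0% |
| Visits scattered in their windows, 0-30% stop over 5 years, any share | 80.5-80.9% | 84.7-85.1% |

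The fourth row is a limiting case. Events and censorings then share the same dates, and ordering events first keeps the risk sets whole. Once visits scatter within ±7 and ±45 days that protection goes: with no events between visits and no early stopping, the rates are 80.7% and 85.1%. With 50% stopping over 5 years the largest shortfalls are 1.9 and 1.7 points.

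Event-free participants lose about 3.5 months on average at 8% per year, or 2.8 months if mammograms count.

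**4. Other times.** At the second interim analysis (COD month 48) the true 3-year tamoxifen rate is exp(-3 × 0.0496) = 86.2%. The rule gives 84.7-85.2% with half to all events between visits, and about 0.1 point low at the other extreme. The 3-year rate at the final analysis differs by only 0.03 to 0.30 points from COD censoring. At month 84, five years after the last randomization, the 4-year gap is 0.02 to 0.04 points.

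**5. Contrast between arms.** The estimated 4-year difference is, for example, 84.7 - 80.5 = 4.2 or 85.1 - 81.1 = 4.0 points, and at most 85.11 - 80.64 = 4.47, against a true 4.0. With equal discontinuation the HR differs by at most 0.004 between the two censoring rules. If 12% versus 6% per year stop, the HR shifts by about 0.5%. With 20% versus 6% it shifts by about 1.6% (0.742 against 0.754) when only visits count as assessments, and little if mammograms count.

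**The case against.** The best reply is that little of importance moves. A reader might set an error of up to 1.8 points against the planned 4-point benefit, or infer that the primary test is compromised. The documents and the calculation support neither: the error is in each arm's level, the two levels move together, and the log-rank test, HR, power and event count stay essentially as planned. The unequal-discontinuation cases have no source in the documents. All of that stands.

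Three further points stand in part.

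- **The 4-year rate is not a named reporting time.** Section 9.2.2 leaves the time points open, and 82% and 86% are sample-size inputs. It is still the natural benchmark for the reported curve.
- **The bias is comparable with or smaller than sampling error.** With 1869 per arm the standard error of a 4-year rate is about 1.0 to 1.1 points. But bias does not average out. A shift of 1.27 against 1.05 is 1.21 standard errors, which would cut the coverage of a nominal 95% interval to about Φ(0.75) - Φ(-3.17) = 77%.
- **Sensitivity analyses are deferred to the SAP.** The supplied document contains only the protocol's summary of the analyses, so it cannot be said that the SAP lacks a corrective analysis, only that the protocol text has none.

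Negative unscheduled assessments would also extend event-free time and narrow the gap. They were not modelled.

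**Conclusion.** The point holds for the per-arm Kaplan-Meier rates in the last stretch of follow-up. At 8% per year discontinuation, the 4-year IBCFS rates at the month-60 analysis are low by about 0 to 1.8 points, and the 3-year rate at the second interim analysis by about 0.1 to 1.5 points. The direction follows from the text of 9.2.2 and the Schedule of Activities. The size depends on the share of events dated between visits and on discontinuation, neither of which the documents give. The zero end requires events to be dated at visits held on their nominal days.

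The absolute difference between arms moves about 0 to 0.5 points. It would be wrong to conclude that the hypothesis test, the HR or the power needs changing. The effect is also temporary: it has nearly gone from the 4-year rate by the 5-year follow-up analysis, although the primary report comes earlier. A supportive analysis is the proportionate response.

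**What to change.** Keep the current rule for the log-rank test, the Cox HR and the main curve. In 9.2.2, and by reference for IDFS, DRFS and LRRFS, add a supportive Kaplan-Meier estimate of the event-free rates with one cut-off per participant. The cut-off is the due date of the last scheduled assessment on or before the COD, under the visit schedule that applied before any event, ignoring an end-of-treatment visit triggered by recurrence. Events after that date do not count in this estimate, and everyone else is censored there. Report these rates beside the main ones.

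The wording about the schedule before any event matters. Recurrence stops treatment (7.1.1) and makes an end-of-treatment visit due 30 days later, so a cut-off that follows actual treatment status lets the bias back in: simulated tamoxifen rates are then 81.2-81.7%. Fixed on the earlier schedule, they return to 81.9-82.1% and 85.9-86.1%. Simply censoring everyone at the COD can overshoot (82.5% for tamoxifen with half of events between visits) and presumes that event-free status is known up to the COD.

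The cost is one extra derivation, with no new data or visits. About 3 to 7% of events drop out of the supportive curve, so it and the HR rest on slightly different event sets. An event found at a visit held a few days after its due date can also fall out. Both are reasons to show this estimate beside the main curve rather than in its place.
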